Appendix 3. PGA

PGA Item for Baseline Visit:

Taking your cardiomyopathy into account, would you say the state of your health is:

- Normal, not at all ill;
- Borderline ill;
- Mildly ill;
- Moderately ill;
- Markedly ill;
- Severely ill;
- Among the most extremely ill.

PGA Item for Follow-Up Visits:

Place an X in the box you feel most closely describes any change which you have experienced since beginning the study medication.

Take into account all change, whether or not you believe it is entirely due to drug treatment.

Choose only ONE response.

Since starting the study medication, my cardiomyopathy (HEART FAILURE) is:

- Very Much Improved
- Much Improved
- Minimally Improved
- No Change
- Minimally Worse
- Much Worse
- Very Much Worse

Appendix 4. 6-Minute Walk Test

The walking test should be performed indoors, along a long, flat, straight enclosed corridor with a hard surface that is seldom traveled. The walking course should be 30 meters in length. A 100 foot hallway is, therefore, required. The length of the hallway should be marked every 3 meters. The starting line should be clearly marked with bright colored tape. A treadmill is NOT recommended.

Study Coordinator/Observers: Should be trained using the standard protocol and then supervised before performing the test alone. They should have completed cardiopulmonary resuscitation training.

Required Equipment:

1. Countdown timer/Stopwatch.
2. Mechanical lap counter.
3. Two small cones to mark the turnaround points.
4. A chair that can be easily moved along the walking course.
5. Worksheets on a clipboard.
6. A source of oxygen.
7. Sphygmomanometer.
8. Telephone.
9. Automated electronic defibrillator.

Subject Preparation:

1. Comfortable clothing should be worn.
2. Appropriate shoes for walking should be worn.
3. Subjects should use their usual walking aids for the test (cane, walker, etc).
4. The subject's usual medical regimen should be continued.
5. A light meal is acceptable before early morning or early afternoon tests.
6. Subject should not have exercised vigorously within 2 hours of beginning the test.

Measurements:

1. Where possible, repeat testing should be performed about the same time of day to minimize variability.
2. A “warm-up” period before the test should NOT be performed.
3. The subject should sit at rest for about 10 minutes before the test starts. Complete the first part of the work sheet.
4. Pulse oximetry is optional.
5. Have the subject stand and rate their Baseline dyspnea and overall fatigue using the Borg scale.

The Borg Scale:

- 0 – Nothing at all
- 0.5 – Very, very slight (just noticeable)
- 1 – Very slight
- 2 – Slight (light)
- 3 – Moderate
- 4 – Somewhat severe
- 5 – Severe
- 6
- 7 – Very severe
- 8
- 9
- 10 – Very, very severe (maximal)

Ask the subject what their level of shortness of breath is and then ask what their level of fatigue is.

1. Set the lap counter to zero and the timer to 6 minutes. Assemble all necessary equipment, and move to starting point.
2. Instructions to the subject:

- a. “The object of this test is to walk as far as possible for 6 minutes. You will walk back and forth in this hallway. Six minutes is a long time to walk, so you will be exerting yourself. You will probably get out of breath or become exhausted. You are permitted to slow down, to stop and to rest as necessary. You may lean against the wall while resting, but resume walking as soon as possible as you are able;
 - b. You will be walking back and forth around the cones. You should pivot briskly around the cones and continue back the other way without hesitation. “Now I’m going to show you. Please watch the way I turn without hesitation”;
 - c. Demonstrate by walking one lap yourself. Walk and pivot around a cone briskly;
 - d. “Are you ready to do that? I am going to use this counter to keep track of the number of laps you complete. I will click it each time you turn around at this starting line. Remember that the object is to walk AS FAR AS POSSIBLE in 6 minutes, but don’t run or jog;
 - e. Do you have any questions?
 - f. Start now or whenever you are ready.”
3. Position the subject at the starting line. You should also stand near the starting line during the test. Do not walk with the subject. As soon as the subject starts to walk, start the timer.
 4. Do not talk to anyone during the walk. Use an even tone of voice when using the standard phrases of encouragement. Watch the subject. Do not get distracted and lose count of the laps. Each time the participant returns to the starting line, click the lap counter once (or mark the lap on the worksheet). Let the participant see you do it. Exaggerate the click using body language, like using a stop-watch at a race.
 - a. After the first minute, tell the subject the following (in an even tone) **“You are doing well. You have 5 minutes to go.”**
 - b. When the timer shows 4 minutes remaining, tell the subject the following: **“You have 4 minutes to go.”**
 - c. When the timer shows 3 minutes remaining, tell the subject the following: **“You are doing well. You are half way done.”**
 - d. When the timer shows 2 minutes remaining, tell the subject the following: “Keep up the good work. You have only 2 minutes left.”
 - e. When the timer shows only 1 minute remaining, tell the subject: **“You are doing well. You have only 1 minute to go.”**

- f. Do not use other words of encouragement (or body language to speed up).
 - g. If the subject stops walking during the test and needs a rest, say this: **“You can lean against the wall if you would like; then continue walking whenever you feel able.”** Do not stop the timer. If the subject stops before the 6 minutes are up and refuses to continue (or decides that they should not continue), wheel the chair over for the subject to sit on, discontinue the walk, and note on the worksheet the distance, the time stopped and the reason for stopping prematurely.
5. Post-test: Record the post walk Borg dyspnea and fatigue levels and ask this: **“What, if anything, kept you from walking farther?”**
 6. If using a pulse oximeter, measure SpO2 and pulse rate from the oximeter and then remove the sensor.
 7. Record the number of laps from the counter (or tick marks from the worksheet).
 8. Record the additional distance covered (the number of meters in the final partial lap) using the markers on the wall as distance guides. Calculate the total distance walked, rounding to the nearest meter, and recording it on the worksheet.
 9. Congratulate the subject on a good effort and offer a drink of water.

1. AMENDMENTS FROM PREVIOUS VERSION(S)

- **Status of study when amendment made:**

Study is ongoing and remains blinded.

- **Details of Changes and Rationale:**

Amendment 1 (SAP Version 2)

Section of the SAP	Summary of change	Rationale
Various sections	Typographical corrections and clarifications For example: Changed “patients” to “subjects” for consistency.	Corrected minor typographical errors and inconsistent terminology.
2.1 Study Design	
 • Clarified specification of sample size as 400 subjects. • Specified the duration of 30 months to be equal to 910 days. 	Inserted new text from protocol amendment 1.
5.6.2. Deviations Assessed Post Randomization	Added use of 3 prohibited medications, ie, diflunisal, tauroursodeoxycholate, and doxycycline as criteria for exclusion from Per-Protocol Analysis Set.	Use of prohibited medication as described in protocol amendment 1 Section 5.8.1. Contraindicated Therapies.
6.1.4. Exploratory Endpoints	Added echo strain and other parameters.	Inserted new text from protocol amendment 1.
8.1.1. Finkelstein Schoenfeld Analyses	
 • Clarified text around algorithm involving “censored” subjects. • Removed sentence related to analysis of “indeterminate” events. 	
 • Modified text to improve clarity. • Removed sentence regarding analysis of events adjudicated as “indeterminate” as it was inconsistent with the last sentence of the first paragraph of Section 8.1.1.
8.2.2. Key Secondary Analyses	Added specification of pattern mixture analysis as a supplemental analysis of the key-secondary analyses.	Inserted new text per agreement with FDA.
8.2.3. Secondary Analyses	Added a statement describing the handling of deaths adjudicated as “indeterminate” similar to the handling of “hospitalizations”.	Added missing detail for handling “indeterminate” deaths in the analysis.
8.2.4. Exploratory Analyses	
 • Added analysis of placebo vs 80 mg randomized subjects who were not downtitrated as requested by PMDA. • Added analysis by region as requested by FDA. • Added additional exploratory endpoints. 	
 • Added analysis requested by PMDA and FDA. • Added exploratory endpoints to be consistent with protocol amendment 1.

Table 2 Summary of Proposed Efficacy and Safety Analyses	Updated to reflect the changes to SAP.	Table updated to be consistent with the body of SAP and protocol amendment 1.
Appendix 1.2. Sample SAS Code for Analyses	
 Added code for pattern-mixture. Made a minor correction to the SAS code for analyses described in Section 8.1.3, ie, added RANDOM statement. 	
 Added SAS code for new pattern-mixture analysis consistent with May 2014 agreement with FDA. Made minor correction to previous SAS code.

Amendment 2 (SAP Version 3)

Section of the SAP	Summary of change	Rationale
Sections 2.1, 8.1.1, 8.1.2, 8.2.4	Cardiac mechanical assist device was added as a reason for discontinuation and treated similar to heart transplant in the analysis.	Cardiac mechanical assist device is indicative of end stage disease similar to a heart transplant.
Section 8.2.5	Removed specification of an unnecessary table.	Listing of adverse events occurring during the trial will include those that start prior to randomization.

Amendment 3 (SAP Version 4)

Section of the SAP	Summary of change	Rationale
Sections 6.4, 8.1.1, 8.1.2, 8.1.3, 8.1.4, 8.1.5, 8.1.6, 8.2.4	NYHA baseline classification categories were change from “NYHA class I and NYHA classes II and III combined ” to “NYHA classes I and II combined and NYHA class III”.	
Redefined the baseline groupings for New York Heart Association (NYHA) Functional Classification that will be used for efficacy analyses, grouping subjects with NYHA Class I and II together to be compared against NYHA Class III.
 
Given the very low number of enrolled subjects with NYHA Class I, the NYHA baseline groupings were redefined for efficacy analyses. This permits a more appropriate baseline adjustment in the primary analysis as well as other secondary and exploratory analyses.

Section 2.1	Study number of the extension study included and other edits.	Edits to reflect the changes to the protocol.
Section 6.1.4, Section 8.2.4, Table 2	KCCQ subjects symptoms subscales clarified.	Better delineated the analysis planned for Kansas City Cardiomyopathy Questionnaire (KCCQ) scores related to subject symptoms.
Section 6.2	Text updated to be consistent with protocol.	The italicized text was update to be consistent with protocol.

Section 8.1.1, Section 6.4	Clarification of how subjects incorrectly classified during randomization will be handled in the primary analysis.	Subjects who were incorrectly classified during randomization will be analyzed using the correct value of the stratification factors (TTR Genotype or NYHA baseline classification) in the primary analysis.
Section 8.2	Frequency of TTR mutation analysis added.	Frequency of various TTR mutations enrolled in the study will be summarized.
Section 8.2.1, Section 8.2.4	Clarified the term “down-titration” to “dose reduction”.	Wording modified per protocol to more accurately represent the change in dose that may occur when a subject is unable to tolerate the randomized dose.
Section 8.2.4	Cross-tabulation summary added for Patient Global Assessment.	Additional descriptive summary for Patient Global Assessment added.
Section 8.2.5	A lag of 28 days will be used in determining treatment-emergence.	Clarifying and documenting a program wide standard procedure with respect to lag.
Appendix 1.2	Visit window algorithm details added.	An algorithm was added to detail how early termination visits will be assigned to nominal study visits.

Amendment 4 (SAP Version 5)

Section of the SAP	Summary of change	Rationale
6.1.4. Exploratory Endpoints	Updated KCCQ related domain and summary scores.	Updated to be consistent with the developers’ names for the KCCQ domain and summary scores.
8.1.1. Finkelstein Schoenfeld Analyses	Corrected an error in the notation (replace subscript “i” with “j”) describing the calculation of U_i .	Update to correct a minor error in the equation describing calculation of U_i ($U_i = \sum_{j \in A_k} u_{ij}$)
8.2.2. Key Secondary Analyses	Updated reference for sample SAS code for pattern mixture analysis from Appendix 1.2 to Appendix 1.3 .	Updated to correct the referenced Appendix number.
8.2.4. Exploratory Analyses	Removed exploratory analysis comparing subjects reduced to 40 mg vs placebo.	The analysis is not meaningful given the very low number of total blinded dose reductions in the study.
8.2.4. Exploratory Analyses	Added tables summarizing plasma concentrations of tafamidis and a listing of plasma concentration of diflunisal.	Added plasma based summary tables for tafamidis and listing for diflunisal.
8.2.5. Safety Analyses	Added by-gender summary tables for treatment-emergent adverse events and serious adverse events.	Added analyses evaluating gender based differences in adverse events between the study treatments.
Table 2	Updated KCCQ related domain and summary scores.	Updated to be consistent with the developers version of KCCQ.
Appendix 1.2	Updated windowing for Echocardiogram endpoints.	Added details of the windowing algorithm for Echocardiogram endpoints based on the study visits when they were collected.

Appendix 1.3	Updated sample SAS code for pattern mixture code.	Update code to fix an error in the ESTIMATE statement in the sample SAS code.
Appendix 1.3	Updated sample SAS code to use PROC GLM replacing PROC ANOVA.	Replaced PROC ANOVA with, PROC GLM which is a more appropriate procedure for un-balanced data.
Appendix 1.4. Details of Multiple Imputation Method to be Used in Sensitivity Analysis	Details to text and SAS code added.	Added details to text and SAS code to improve clarity.

2. INTRODUCTION

Amyloidosis is a severely debilitating condition induced by the accumulation of various insoluble fibrillar proteins, or amyloid, within the tissues in amounts sufficient to impair normal function. Different precursor proteins have been associated with amyloid cardiomyopathy, including immunoglobulin light chains (associated with primary or AL amyloidosis), serum amyloid A (associated with secondary or AA amyloidosis) and transthyretin (TTR) representing the most common inherited amyloidosis. Transthyretin (also referred to as pre-albumin), a 127-amino acid, 55 kDa protein that is primarily synthesized in the liver, is a transport protein of thyroxine and retinol-binding protein-retinol (vitamin A) complex (Blake 1978, Monaco 1995). A mutation in TTR accelerates the process of fibrillogenesis whereby the tetrameric structure of the TTR protein dissociates leading to amyloid deposition (Nilsson 1975, Saraiva 2001). Dissociation of the TTR tetramer into monomers is the initial and rate-limiting step in amyloidogenesis (Nilsson 1975, Saraiva 2001).

Transthyretin amyloidosis can present as either a hereditary or an age-related disease. The major phenotypic presentations of TTR amyloidosis include transthyretin familial amyloid polyneuropathy (TTR-FAP), which can present with sensorimotor and autonomic polyneuropathy and transthyretin cardiomyopathy (TTR-CM), which can present in either a genetic variant or a wild-type form (the latter is also known as senile systemic amyloidosis or SSA).

Median survival from diagnosis for patients with TTR-CM was 41 months in a study of the V122I mutation and median survival was reported as 46 months for wild-type (Connors 2011). Death in most patients with cardiac amyloidosis is from cardiac causes, including sudden death, heart failure, and myocardial infarction (Kyle 1996, Smith 1984).

Tafamidis is an oral small molecule, under development by Pfizer, as a disease modifying therapy for TTR amyloid diseases. It binds to the thyroxine binding sites on the TTR tetramer, thereby preventing destabilization into the monomeric form. In study Fx1B-201, tafamidis effectively stabilized TTR in 34 of 35 (97.1%) subjects, representing both wildtype and V122I, at Week 6, with approximately 88% stabilized throughout the 12 months of the study. Of note, tafamidis has also been studied in TTR-FAP and effectively stabilized TTR in 98% of subjects as well as demonstrating effects relative to placebo on clinical measures (Coelho 2012).

TTR-CM is a rare disease with very little available published information. Based on this, the natural history and disease progression of TTR-CM were prospectively evaluated in a noninterventional study involving 29 subjects (Transthyretin Amyloidosis Cardiac Study [TRACS]; Study Fx-001; Ruberg 2012). In addition, subsequent to the TRACS study, an open-label, Phase 2 Study Fx1B-201 was initiated. This study involved 35 subjects with TTR-CM who received open-label tafamidis 20 mg QD for 12 months along with routine standard of care. The proportion of patients with the variant genotype was substantially lower in Fx1B-201 compared with TRACS.

2.1. Study Design

This is a Phase 3, multicenter, international, three-arm, parallel design, placebo-controlled, randomized study with a 30-month double-blind treatment phase, to determine efficacy, safety and tolerability of tafamidis on clinical outcomes in subjects with either transthyretin genetic variants or wild-type transthyretin resulting in amyloid cardiomyopathy (TTR-CM).

There will be approximately 400 subjects enrolled in the study in a 2:1:2 ratio (placebo:20 mg:80 mg). The subjects will be allocated to the 3 arms of the study in the following manner: n=160 in the placebo arm, n=80 in the 20 mg arm, and n=160 in the 80 mg arm. Subjects who experience adverse events that may be associated with poor tolerability to treatment with tafamidis that may impact dosing adherence have the option of blinded treatment re-assignment and potential dose-reduction (see [Section 5.5 of protocol](#)). Subjects will be stratified during enrollment by TTR genotype (variant and wild-type) and structured such that greater than 30% of randomized subjects have a TTR mutation and greater than 30% of subjects have a diagnosis of wild-type TTR cardiomyopathy, with the intent to enroll comparable numbers between the variant and wild-type groups.

Enrollment may be closed for either wild-type or variant stratum in order to enroll at least 30% of subjects with each TTR genotype (wild-type and variant).

Additionally, stratification to treatment assignment will be done for Baseline severity of disease based on NYHA classification (NYHA Class I and NYHA Classes II and III combined). Stratification will be implemented in order to maintain a balance of both TTR genotype and disease severity across the treatment assignments. The site will ensure a Month 30 follow-up contact to determine the subject's vital status and whether the subject has had a heart and / or liver transplant or implantation of cardiac mechanical assist device. Upon completion of the study at the Month 30 visit, subjects may be eligible for treatment with tafamidis in a separate study (B3461045), which will permit the collection of additional safety and efficacy data, and may include the assessment of hospitalizations, mortality, and other outcomes relating to disease progression. For the purpose of this study, 30 months is defined as 910 days. Eligibility for the extension study (B3461045) requires subject participation in this study at least through Day 896 (Month 30 minus 2 weeks).

2.2. Study Objectives

The primary objective of this study is to assess the efficacy of an oral dose of 20 mg or 80 mg tafamidis meglumine soft-gel capsules based on all-cause mortality and on frequency of cardiovascular-related hospitalizations as well as to assess safety and tolerability in comparison to placebo. Tafamidis or placebo will be administered once daily, in addition to standard of care, for 30 months in subjects diagnosed with variant or wild-type TTR cardiomyopathy (TTR-CM).

3. INTERIM ANALYSES, FINAL ANALYSES AND UNBLINDING

No formal efficacy interim analysis is planned.

The E-DMC will be responsible for ongoing monitoring of the safety of subjects in the study according to the E-DMC Charter through safety interim analyses consisting of comparisons of safety information across treatment groups. Un-blinded descriptive summaries of mortality, hospitalization, adverse events, laboratory data, and other safety monitoring data as requested by the E-DMC will be provided for their review.

4. HYPOTHESES AND DECISION RULES

4.1. Statistical Hypotheses

The null hypothesis for the primary analysis is that neither all-cause mortality nor frequency of cardiovascular-related hospitalizations is different between the tafamidis and placebo treatment groups. The corresponding alternative hypothesis is that at least one and possibly both all-cause mortality and frequency of cardiovascular-related hospitalizations are different between the tafamidis and placebo treatment groups.

4.2. Statistical Decision Rules

All hypothesis testing will be conducted using two-sided tests with $\alpha = 0.05$ level of significance. The list of key-secondary endpoints and the methodology for controlling the study-level Type I error at 0.05 due to multiple analyses are detailed in [Section 8.2.2](#).

5. ANALYSIS SETS

The following sets are defined for use in the analyses:

- Intent-To-Treat (ITT) Analysis Set;
- Per-Protocol (PP) Analysis Set;
- Safety Analysis Set.

Both the ITT and PP analysis sets will be used for the primary analysis and for the analyses of the key-secondary endpoints, with the ITT being primary. The secondary endpoints and the exploratory endpoints will only be analyzed using the ITT analysis set. The Safety Analysis Set will be used in the analyses of the safety data.

5.1. Intent-to-Treat Analysis Set

The intent-to-treat (ITT) analysis set will include all subjects in the safety population who had at least 1 post Baseline efficacy evaluation (ie, post Baseline hospitalization, study visit, or date of death). This may also be referred to as a modified intent-to-treat group but for simplicity will be referred to throughout the protocol and SAP as ITT.

5.2. ‘Per Protocol’ Analysis Set

The per protocol (PP) analysis set will include all subjects in the ITT set who did not violate inclusion/exclusion criteria and who did not have protocol violations considered to impact the interpretation of the primary efficacy analysis.

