9.2. Analysis Populations

The intent-to-treat (ITT) analysis set will include all subjects in the safety population who had at least 1 post Baseline efficacy evaluation (ie, post Baseline hospitalization, study visit, or date of death). This may also be referred to as a modified intent-to-treat group but for simplicity will be referred to throughout the protocol and SAP as ITT. The per protocol (PP) analysis set will include all subjects in the ITT set who did not violate inclusion/exclusion criteria and who did not have protocol violations considered to impact the interpretation of the primary efficacy analysis. The safety analysis set will include all subjects who are enrolled (randomized) and received at least 1 dose of double-blind medication.

Both the ITT and PP analysis sets will be used for the primary analysis and for the analyses of the key secondary endpoints, with the ITT being primary. The secondary endpoints and the exploratory endpoints will only be analyzed using the ITT analysis set. The Safety Analysis Set will be used in the analyses of the safety data.

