The term “censored” refers to a subject who discontinues from the trial for reasons other than death. For such subjects, there will be additional follow-up to obtain vital status (and transplant / cardiac mechanical assist device status) at Month 30 and that information will be used in the analysis. In the case where one subject is censored before a second subject has died, and where the vital status of the first subject at Month 30 is missing, then the frequency of cardiovascular-related hospitalizations at the shorter of their follow-up times (the shorter of the 2 subjects’ study participation) will be used in assigning a +1 or -1. In the simpler case

where one subject drops out but both are known to be alive at Month 30, the frequency of cardiovascular-related hospitalizations, at the shorter of their follow-up times (the shorter of the 2 subjects study participation), will be used in assigning a +1 or -1. Comparisons of cardiovascular related hospitalization frequency for subjects who completed all 30 months study duration will be based on the earlier of the two actual study durations (days).

Subjects, who discontinue for transplantation (ie, heart transplantation and combined heart and liver transplantation) or for implantation of a cardiac mechanical assist device, will be handled in the primary analysis in the same manner as death. More specifically, the time of the transplant or cardiac mechanical assist device implant will be used in the subject-to-subject comparison in the same manner as if the subject had died at that time (regardless of any additional vital status follow-up information). Data from subjects who drop out for a liver-only transplantation will be handled in the same manner as the data from all other censored subjects.

To examine the potential effect of including heart transplantation or cardiac mechanical assist device as “deaths” in the primary analysis, a sensitivity analysis will be performed treating all transplantation or cardiac mechanical assist device in the same manner as any other censored observation.

As an additional sensitivity analysis, a multiple imputation analysis will be applied using the method developed by Rubin (Rubin 1987). Combined results will be provided for the primary analysis (ie, using Finkelstein-Schoenfeld) as well as for the separate mortality and morbidity elements. Details are provided in the SAP.

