5.3. Safety Analysis Set

The safety analysis set will include all subjects who are enrolled (randomized) and received at least 1 dose of double-blind medication.

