5.5. Treatment Misallocations

For subjects, who were not treated, not randomized, or received incorrect treatment, the following rules will be used:

- Randomized but not treated, then they will be excluded from the ITT and PP analysis sets for efficacy evaluations and excluded from the safety analyses as actual treatment is missing.
- Treated but not randomized, then by definition they will be excluded from the efficacy analyses since randomized treatment is missing, but will be reported under the treatment they actually received for all safety analyses.
- Randomized but took incorrect treatment, then they will be reported under their randomized treatment group for all efficacy analyses, but will reported under the treatment they actually received for all safety analyses.

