The term “censored” refers to a subject who discontinues from the trial for reasons other than death. For such subjects, there will be additional follow-up to obtain vital status (and transplant status / cardiac mechanical assist device status) at Month 30 and that information will be used in the analysis. In the case where one subject is censored before a second subject has died, and where the vital status of the first patient at Month 30 is missing, then the frequency of cardiovascular-related hospitalizations at the shorter of their follow-up times (the shorter of the 2 subjects’ study participation) will be used in assigning a +1 or -1. In the simpler case where one subject drops out but both are known to be alive at Month 30, the frequency of cardiovascular-related hospitalizations, at the shorter of their follow-up times (the shorter of the 2 subjects study participation), will be used in assigning a +1 or -1. Comparisons of cardiovascular related hospitalization frequency for subjects who completed all 30 months study duration will be based on the earlier of the two actual study durations (days).

Subjects, who discontinue for transplantation (ie, heart transplantation and combined heart and liver transplantation) or for implantation of a cardiac mechanical assist device, will be handled in the primary analysis in the same manner as death. More specifically, the time of the transplant or cardiac mechanical assist device implant will be used in the subject-to-subject comparison in the same manner as if the subject had died at that time (regardless of any additional vital status follow-up information). Data from subjects who drop out for a liver-only transplantation will be handled in the same manner as the data from all other censored subjects.

The proposed test is a score test based on the sum of the scores for the treated group. A value of $D_i = 1$ for subjects in tafamidis and $D_i = 0$ for subjects in the placebo group. Using the u_{ij} for every pair of subjects defined above, we assign a score to each subject.

The subjects are divided into 4 strata $k = 1; 2; 3, 4$. If A_k is the set of indices of the n_k subjects in the k^{th} strata and that U_i is calculated within strata (for $i \in A_k; U_i = \sum_{j \in A_k} u_{ij}$), then the test statistic is based on

$$T = \sum_k \sum_{i \in A_k} D_i U_i$$

Let m_k be the total number of subjects in the k_{th} stratum who are in the tafamidis group. Then in k_{th} strata

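### A dosed subject with no post-baseline visit enters the primary ITT set if dead or hospitalised but not if confirmed alive at Month 30: low severity, and free to fix

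*SAP*

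**What the plan says.** The rule has two steps. The subject must be in the safety set, defined in SAP 5.3 as "all subjects who are enrolled (randomized) and received at least 1 dose of double-blind medication". The subject must then have "at least 1 post Baseline efficacy evaluation (ie, post Baseline hospitalization, study visit, or date of death". Protocol 9.2 has the same rule: "all subjects in the safety population who had at least 1 post Baseline efficacy evaluation". Three things qualify, and being known to be alive is not one of them. Both documents disclose the departure from strict ITT: "This may also be referred to as a modified intent-to-treat group".

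SAP 5 uses both ITT and per-protocol sets for the primary and key secondary analyses, "with the ITT being primary". SAP 5.4 defines no other set, and SAP 8.2.4 lists no all-randomised sensitivity analysis.

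For subjects who were never dosed, SAP 5.5 states: "Randomized but not treated, then they will be excluded from the ITT and PP analysis sets for efficacy evaluations".

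For subjects who discontinue other than by death, SAP 8.1.1 says "there will be additional follow-up to obtain vital status (and transplant status / cardiac mechanical assist device status) at Month 30", and that this information enters the analysis. Protocol 9.2.1 agrees: "there will be additional follow-up to obtain vital status". In the pairwise scoring, a living subject gets +1 against a dead one.

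**The concern.** Take two subjects who each take one dose and leave before any visit or hospitalisation. Site follow-up finds one dead and the other alive at Month 30. The first has a date of death and enters the ITT set. The second has nothing on the list and does not. Among such leavers who are never hospitalised, only deaths are represented. Membership of the primary set then turns on mortality, which is the first thing the primary test compares.

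The two SAP sections also pull against each other. Section 8.1.1 intends Month 30 vital status to be used for discontinued subjects, but Section 5.1 removes these survivors before that rule can act. The missing-data provisions do not bring them back: SAP 7 imputes nothing for the primary analysis, and the multiple imputation in SAP Appendix 1.4 imputes hospitalisation counts only.

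At stake is measured mortality in an arm that loses subjects before any visit, and the between-arm comparison if the arms lose them at different rates. Dropping untreated subjects is a separate matter: it applies whether they live or die, but it also takes the primary set away from the randomised groups.

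**Working it through.** **Inputs.** Protocol 9.1 gives placebo mortality of 25%; tafamidis mortality of 12.5% (base) or 17.5% (conservative); 2.5 against 1.5 cardiovascular admissions per subject; 30 months; two-sided 0.05; and N = 400, which is 160 placebo against 80 + 160 = 240 tafamidis. The share *x* of dosed subjects with no visit is not in the documents. I assume 1% to 5% in the formula and 0% to 10% in the simulation.

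**Mortality within one arm.** Let mortality be *p*, the same in leavers and others. Of the share *x*, dead leavers (*xp*) stay and living leavers (*x*(1−*p*)) are dropped. Measured mortality is *p* / (1 − (1−*p*)*x*). With *p* = 0.25:
- *x* = 1%: 0.25 / 0.9925 = 25.2%
- *x* = 2%: 0.25 / 0.985 = 25.4%
- *x* = 5%: 0.25 / 0.9625 = 26.0%

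These are ceilings for leavers who die at the arm's rate, because a living leaver who was hospitalised stays in. If leavers die more often than the arm the figure falls. If they die less often it rises, to at most 0.25 / 0.95 = 26.3% at 5%.

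**Head count.** Across 400 subjects, 2% is 8 leavers (about 2 deaths kept, 6 survivors dropped) and 5% is 20 (about 5 kept, 15 dropped). One placebo leaver in 160 (0.625%) gives 0.25 / (1 − 0.75 × 0.00625) = 25.1%.

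**Difference between arms, true 25% against 12.5%.** With 5% in both arms, tafamidis shows 0.125 / (1 − 0.875 × 0.05) = 13.1%. The difference is 26.0 − 13.1 = 12.9 points against a true 12.5. With 5% in placebo only, it is 26.0 − 12.5 = 13.5.

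**Effect on the test.** I simulated the SAP 8.1.1 statistic. The plan's power figures (96%, 80%, 90%) cannot be reproduced from its stated inputs alone, because the count distribution is not given: plain Poisson counts give 100%, 99% and 100%. Negative binomial counts with an assumed dispersion parameter k = 0.75 give 95.7%, 79.1% and 89.2%, so I used that value. Other assumptions are exponential survival, a single stratum, leaving unrelated to outcome, vital status always obtained, and every living leaver dropped under the SAP rule. The null case has 25% mortality and 2.5 admissions in both arms, N = 400 and 8,000 runs (standard error about 0.002 on the one-sided rates):

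| No-visit share, placebo / tafamidis | Error favouring tafamidis, SAP rule | Same, all kept | Two-sided error, SAP rule |
|---|---|---|---|
| 2% / 2% | 0.028 | 0.026 | 0.053 |
| 5% / 5% | 0.028 | 0.023 | 0.054 |
| 5% / 0% | 0.037 | 0.025 | 0.056 |
| 0% / 5% | 0.018 | 0.024 | 0.056 |
| 10% / 2% | 0.043 | 0.025 | 0.056 |

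Nominal one-sided error is 0.025. The mean Z is about 0 with equal loss, +0.16 at 5% / 0% and −0.18 at 0% / 5%. Power with a 30% mortality reduction, SAP rule against all kept (6,000 runs), is 0.868 against 0.876 at 5% / 5%, 0.914 against 0.881 at 5% / 0%, and 0.855 against 0.896 at 0% / 5%.

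**The case against.** The strongest reply is that hardly anyone is affected. A survivor is dropped only if dosed and without a Week 2 visit (which may be a telephone call, Schedule of Activities note a), a Month 1 visit, an early-discontinuation visit (Protocol 6.2.13) or any hospitalisation. A 5% share in placebo means 8 such subjects, and nothing in the documents suggests that many. This stands, and it is why the point is low severity.

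A second reply is that the Month 30 vital-status check is itself a study visit, since Protocol 6.2.13 lists it among that visit's procedures. On that reading the asymmetry disappears. But Protocol 3 calls it a follow-up contact, and neither document says that it qualifies a subject for ITT. One sentence would settle it.

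A reader might infer three stronger things, none of which the documents support:
- **That dropping untreated subjects also selects on outcome.** SAP 5.5 excludes them whether they live or die. Randomisation and dispensing fall in the same blinded Baseline visit (Protocol 6.2.1), so such subjects should be few.
- **That the rule by itself biases the treatment comparison.** It applies alike to both arms. With equal early loss the simulation shows no material inflation, and two-sided error stays between 0.047 and 0.056 in every scenario run. The documents give no reason to expect blinded arms to differ in loss this early.
- **That Month 30 status will be known for everyone.** Protocol 6.3 makes registry searches subject to availability and local law, and SAP 8.1.1 provides for missing status.

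Nor is the label hidden: both documents say the set could be called modified ITT.

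**Conclusion.** The point holds on the text. For dosed subjects with no visit, entry to the primary set depends on outcome, and SAP 5.1 conflicts with the use of vital status in SAP 8.1.1. Excluding untreated subjects is a second, separate departure that depends on dosing. At 25% mortality the distortion within an arm is at most 0.2, 0.4 and 1.0 points for no-visit shares of 1%, 2% and 5%, if leavers die at the arm's rate. Those shares are assumptions, and the true share is probably at the low end. Material bias between arms needs unequal early loss, and its direction follows whichever arm loses more. This is a free improvement of low severity, not a threat to the trial's conclusion.

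**What to change.** Define the set for the primary and mortality analyses as all randomised subjects, analysed as randomised. A subject with no visit enters on available Month 30 vital status and zero hospitalisation follow-up. The pairwise rules already cover this: if alive, the subject beats the dead and ties with the living, because counts are compared at the shorter follow-up, which is zero. Where vital status is missing, the censoring rules in SAP 8.1.1 apply unchanged.

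At minimum, add known Month 30 vital status to the qualifying evaluations and add an all-randomised sensitivity analysis.

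Keep the present set, named modified ITT, for the 6-minute walk and KCCQ. Keep it also for the Poisson models, whose log-duration offset (SAP Appendix 1.3) is undefined at zero follow-up.

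The cost is wording in SAP 5.1 and 5.5, Protocol 9.2 and the protocol summary, settled before unblinding. No new data are needed: vital status is already sought for every subject, and the release form required at entry (Protocol 4.1) counts its 30 months from randomisation.
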